7. HANDLING OF MISSING VALUES

Data based on entire scales which are missing will be analyzed as follows:

If the data are time until event data and there is no observed event (at any point during the trial) the observation will be censored at the last observation. If there was an observed event, the data associated with the first observation of that event will be used, all other observations will not be needed.

For all change from baseline analyses, the data will be analyzed as follows: for analyses at each visit, the missing observations will not be used as the models will be estimated using an Mixed Model Repeated Measure (MMRM) model for the analysis.

7.1. Norfolk Quality of Life – Diabetic Neuropathy (QoL-DN)

If missing responses to questions occur, missing scores will be imputed as the mean of the non-missing questions within the domain for that visit as long as at least 60% of the items within the domain have a non-missing response. The domain score will then be the sum of the non-missing and imputed questions. If all 35 questions are non-missing or imputed as defined above, then the TQOL will be calculated as the sum of the non-missing items and the imputed values. If questions could not be imputed as defined above due to less than 60% of responses in a domain; however, at least 60% of the total questions are either non-missing or imputed, then the TQOL will be calculated as the mean of the non-missing and imputed questions times 35. If greater than 40% of the items in a domain or TQOL are missing, then the domain is deemed missing.

7.2. Neuropathic Impairment Score (NIS)

If any question is answered as ‘N/A’ then the score for that question will be 0. Additional missing imputation rules are provided in [Appendix 1.1](#).

7.3. The Karnofsky Performance Scale Index

The Karnofsky Performance Scale Index is a single item scale, and, as such; missing values will be excluded from analyses.

7.4. Assessment of Subject Ambulation

If the first available assessment indicates no impairment of ambulation, then all previous missing assessments will be set to no impairment of ambulation. However, if the first available assessment indicates any level of impairment then all previous missing assessments will remain as missing.

If an assessment is missing but there are assessments surrounding the missing assessment and the assessments surrounding the missing assessment are the same, the missing assessment will be set to that value. If the assessment before the missing assessment is different from the assessment after the missing assessment, then the missing assessment will be excluded from the analyses. Missing assessment after the date of change or start of ambulatory status will be set to the value last seen with the change or start of the status.

Changes in ambulatory assessment that are noted as due to circumstances unrelated to disease progression (determined either through investigator determination or clinical definition) will be set to the status last seen for that subject for that visit; an example would be: leg fracture requiring crutches.

8. STATISTICAL METHODOLOGY AND STATISTICAL ANALYSES

8.1. Statistical Methods

8.1.1. Analyses for Continuous Data

All continuous data will be summarized with descriptive statistics, including mean, standard deviation, median, range and 95% confidence intervals. In addition, change from baseline statistics will be presented as appropriate, to include the appropriate descriptive statistics. For the change from baseline statistics, the estimate will be adjusted for baseline (where appropriate) and the LSMean and standard error will be presented with the 95% confidence interval.

These summaries will be provided by treatment group and by TTR mutation.

For the V30M subjects, a repeated measures analysis of covariance model with change from baseline as the dependent variable, an unstructured covariance matrix, treatment, month and treatment-by-month as fixed effects, baseline as covariate and subject as a random effect in the model will be used to estimate the LSMeans and confidence intervals as indicated above. A sensitivity analysis will also be conducted using the model shown above however, without baseline as a covariate. See [Appendix 1.7](#) for an example of the SAS code for this analysis.

In the event that the model will not converge due to the limited amount of data at the later visits, the model will be evaluated up to the point that it will converge. The data after that

point will be summarized using descriptive statistics only and for the T-T and P-T groups will not be compared and no p value will be produced.

Separate analyses will be conducted using both measurements of baseline, at study start and at active treatment start as specified above. Due to the 18 month length of Fx-005 and the fact that many of the outcomes are measured annually, the measurements aren't at the same time points (for example, 3 years of active treatment); this disparity of treatment schedules will not allow a direct comparison of the subjects' change from baseline on active treatment, at any time point after the parent trials; therefore, just descriptive statistics will be reported for the outcomes measured annually.

For the non V30M subjects, a repeated measures analysis of covariance model with change from baseline as the dependent variable, an unstructured covariance matrix, month as fixed effect, baseline as covariate and subject as a random effect in the model will be used to estimate the LSMeans and confidence intervals. A sensitivity analysis will also be conducted using the model shown above however, without baseline as a covariate.

8.1.2. Analyses for Categorical Data

All categorical data will be summarized as n, percentage and 95% confidence intervals. These summaries will be provided by treatment group and by TTR mutation. Separate analyses will be conducted using both measurements of baseline, at study start and at active treatment start as specified above.

Confidence intervals will be based on estimates of the binomial probabilities with no adjustments to the probabilities.

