### **2.2. Endpoints**

The efficacy endpoints for this study are:

- The Neuropathy Impairment Score (NIS);
- The Total Quality of Life (TQOL) score as measured using the Norfolk Quality of Life for diabetic neuropathy (QOL-DN) questionnaire;
- The Karnofsky Performance Scale Index;
- Assessment of subject ambulation.

The safety endpoints for this study are:

- The incidence of treatment-emergent adverse events (TEAEs), physical examinations, clinical laboratory testing, use of concomitant medications, ECGs and vital signs

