### **3.2. Study Duration and Dates**

The study will continue for up to 10 years or until subject has access to tafamidis for TTR-FAP via prescription. Upon regulatory approval for the treatment of TTR-FAP in their respective country and access to prescription tafamidis, subjects may be withdrawn from the study. The decision to withdraw subjects in a country will be done in consultation between the investigator and the sponsor (see Section 6.3).

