6.3. Adverse Events

Treatment emergent adverse events will be summarized by all causes and treatment relatedness groupings. For the purposes of this study, treatment emergent is defined as an event which begins after enrollment in the current study (B3461023) or which worsens during the course of the current study. In addition, severity of the adverse events will be summarized by all causes and treatment relatedness.

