8.3. Safety Analyses

Safety data will be summarized for the safety analysis population.

Treatment and Disposition of Subjects: Subject evaluation groups will show end of study subject disposition and will show which subjects were analyzed for efficacy, as well as for safety (adverse events and laboratory data). Frequency counts will be supplied for subject discontinuation(s) by treatment.

A listing of treatment duration for each subject will be reported in accordance with the sponsor reporting standards.

Demographic and Baseline Characteristics. A break-down of demographic data will be provided for age, gender, race, weight, body mass index, and height. Each will be summarized by treatment group, sex at birth and 'All Subjects' in accordance with the sponsor reporting standards. All baseline and disease characteristics will also be summarized.

Discontinuations. Subject discontinuations due to adverse events will be detailed and summarized.

Adverse events (AEs): Treatment emergent adverse events will be summarized by causality and severity.

Hematology, Biochemistry and Urinalysis: Descriptive statistics will be provided for each test result and for change from baseline by visit. Additional summaries for abnormalities in laboratory measures will be provided for the following populations: without regard to baseline, abnormal at baseline and normal at baseline.

Baseline is defined in two ways as described above.

ECG: Changes from baseline (defined as the last evaluation prior to the first dose of study drug) will be summarized for each of the ECG measures listed above. In addition, ECG changes from baseline will be categorized as follows:

- a change from baseline \geq 60 msec,
- a change from baseline \geq 90 msec;
- a change from baseline between 30 msec (inclusive) and $<$ 60 msec;
- a reading of greater than 450 msec at any visit;
- a reading of greater than 480 msec at any visit;
- a reading of greater than 500 msec at any visit.

Baseline is defined in two ways as described above.

Note: In Italy only Echocardiograms and Holter Monitoring were performed, and therefore, the Italian subjects will not be included in these summaries.

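### In the visible SAP, TEAE incidence is a crude percentage with no person-time denominator, so over follow-up that varies up to 10 years it mixes risk with time observed

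*SAP*

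**What the plan says.** Protocol 2.2 lists the incidence of TEAEs first among the safety endpoints, and long-term safety is a stated objective (Protocol 2.1, SAP 2.2).

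On analysis, SAP 6.3 says: "Treatment emergent adverse events will be summarized by all causes and treatment relatedness groupings". SAP 8.3 says: "Treatment emergent adverse events will be summarized by causality and severity". Neither section names the statistic. SAP 8.1.2 supplies it: "All categorical data will be summarized as n, percentage and 95% confidence intervals", shown by treatment group and TTR mutation. It adds: "Confidence intervals will be based on estimates of the binomial probabilities with no adjustments to the probabilities". Protocol 9.2 likewise plans counts and percentages for categorical variables. The TEAE clock starts at enrolment in this study (SAP 6.3), and the safety population is enrolled subjects with at least one dose, with post-transplant visits left out of the summaries (SAP 5.2).

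On exposure, SAP 8.3 offers only this: "A listing of treatment duration for each subject will be reported in accordance with the sponsor reporting standards". Kaplan-Meier methods are specified for time to death (6.2.5, 8.1.3) and, if numbers allow, for ambulatory stage (8.2). They are not specified for adverse events.

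On follow-up, Protocol 3.2 says: "The study will continue for up to 10 years or until subject has access to tafamidis for TTR-FAP via prescription". Withdrawal on prescription access is decided by country, and subjects who leave that way count as completers (Protocol 3 and 6.3).

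**The concern.** A binomial percentage describes a risk over a stated period only if everyone is observed for about the same time. Here the period is set by when prescription tafamidis reaches each country, by transplantation and by ordinary withdrawal. A subject who leaves early without an event adds as much to the denominator as one followed to the cap.

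The study exists to describe long-term safety, and its results are meant to be presented at successive interim analyses (Protocol 9.11, SAP 3). Without a time base, a reader cannot tell whether a higher percentage at a later cut means a rising hazard or simply more observation. Nor can it be set against the Fx-005 percentages in Protocol Table 1, which come from an 18-month study.

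**Working it through.** **1. Figures in the plan.** There is no design figure to reproduce: Protocol 9.1 gives no sample size calculation and SAP 4.1 tests no hypothesis. The nearest stated figure is prior exposure in Protocol 1.2.4 (127 patients, mean 538 days). 127 × 538 / 365.25 = 187.1 patient-years and 538 / 30.4375 = 17.7 months, both as stated. The protocol therefore already reports exposure in patient-years for earlier data.

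**2. Crude percentage as a function of time.** With a constant first-event rate λ per year and follow-up of T years, the expected crude percentage is 1 − exp(−λT). The documents give neither λ nor T by group, so both are assumptions here.

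| λ per year | T = 2 years | T = 6 years |
|---|---|---|
| 0.05 | 1 − exp(−0.1) = 9.5% | 1 − exp(−0.3) = 25.9% |
| 0.1 | 1 − exp(−0.2) = 18.1% | 1 − exp(−0.6) = 45.1% |
| 0.2 | 1 − exp(−0.4) = 33.0% | 1 − exp(−1.2) = 69.9% |

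At λ = 0.1 the values at 1 and 10 years are 9.5% and 63.2%. Within a row the hazard is the same throughout.

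**3. A rate taken from the documents.** Protocol Table 1 gives diarrhoea in 17 of 65 tafamidis subjects in Fx-005, an 18-month study. Assuming a constant rate and full follow-up, λ = −ln(1 − 17/65) / 1.5 = 0.202 per year. The crude percentage is then 18.3% at 1 year, 26.2% at 1.5 years, 33.3% at 2, 63.6% at 5 and 86.8% at 10. For a rarer event (4 of 65), λ = 0.0423 and the percentages are 6.2% at 1.5 years, 19.1% at 5 and 34.5% at 10.

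**4. When a contrast between groups is distorted.** Two groups were given the same rate (0.202 per year), with 10,000 simulated studies per scenario. Group sizes and follow-up are assumed. False separation means that the 95% interval for the difference in percentages, or for the rate ratio, excludes no difference.

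| Follow-up, years (group sizes) | Crude % | Rate per person-year | False separation, crude | False separation, rate |
|---|---|---|---|---|
| 2 vs 5 (90, 20) | 33.3 vs 63.5 | 0.203 vs 0.209 | 71.3% | 4.9% |
| uniform 0.5–3.5 vs 2–8 (90, 20) | 32.2 vs 61.4 | 0.204 vs 0.210 | 67.6% | 5.3% |
| uniform 0.5–5 vs 0.5–10 (90, 20) | 40.6 vs 59.8 | 0.204 vs 0.211 | 37.3% | 5.3% |
| uniform 0.5–5 in both (45, 45) | 40.7 vs 40.6 | 0.206 vs 0.206 | 5.4% | 4.9% |

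The distortion comes wholly from unequal follow-up. With equal follow-up the contrast is sound, although each percentage still has no time horizon.

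**5. Interim cuts.** Once enrolment is complete, the denominator is fixed and the number of subjects with at least one event cannot fall. The cumulative percentage can then only stay level or rise from cut to cut, whatever the hazard does.

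**The case against.** The strongest reply is that the study is descriptive. No adverse event contrast is tested (SAP 4.1), V30M and non-V30M are analysed separately (SAP 6.5), and n (%) correctly counts the subjects seen to have an event. That stands, and it is why n (%) should stay. It does not supply a time horizon, and intervals displayed by group invite comparison.

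A reader might infer that the Tafamidis-Tafamidis and Placebo-Tafamidis columns will differ through follow-up alone. The documents do not support this. Both groups come from the Fx-005 randomisation (SAP 4.2) and TEAEs are counted from entry to this study (SAP 6.3), so no systematic difference in observation time is shown.

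A reader might also infer that the two mutation groups have unequal follow-up. This is plausible: V30M patients are concentrated in certain countries (Protocol 1.2), exit is decided by country, and non-V30M evidence comes from a different parent study (Protocol 1.2.4). But no follow-up by group is given.

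It also cannot be said that no other adverse event statistic exists. The list of tables is in a separate addendum (SAP 9) and the appendices are redacted, so the point applies to the visible text.

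The assumed times are open to challenge too. Withdrawal on prescription access is permitted, not required. The latest dated SAP change (September 2014) falls about 5 years after the original protocol (June 2009), so the 6- and 10-year values describe a study that continues beyond that date. The shorter horizons in steps 3 and 4 already show the effect.

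Finally, death, a key harm, does have censored time-to-event analysis. That covers one outcome, not TEAEs.

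**Conclusion.** The point holds for the visible plan. A pooled TEAE percentage with a binomial interval, over follow-up that varies up to 10 years and can be cut off by country, mixes risk with time observed. It is not comparable across interim cuts or with 18-month percentages. It would be too strong to say that it reflects time instead of risk: it reflects both.

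The size depends on the assumed rate and follow-up. Between 2 and 6 years with an unchanged hazard, the percentage rises by a factor of about 2.1 (69.9/33.0) to 2.7 (25.9/9.5) over rates of 0.2 to 0.05 per year. Distortion between V30M and non-V30M is conditional on unequal follow-up, and none is shown between the Fx-005 arms. This is a worthwhile improvement to how the long-term safety objective is reported. No tested conclusion is at risk.

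**What to change.** In SAP 6.3 and 8.3:

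- Keep n (%) for the safety population.
- Add total patient-years at risk to each column.
- Add the number of subjects with a first event per 100 patient-years at risk, with exact Poisson 95% intervals. Do this for all-causality, treatment-related and serious TEAEs, TEAEs leading to discontinuation, and the common preferred terms, by treatment group and mutation.
- Define time at risk to match the TEAE window: start at entry to this study, stop at the first event or the end of adverse event observation, and stop at transplant, since SAP 5.2 drops later visits.
- Give rates by year on study only for the overall and serious TEAE categories. This shows whether the hazard is roughly constant. With up to 110 subjects expected (Protocol 9.1), finer cells would be sparse.

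The cost is SAP wording and a few additional tables, with no new data collection. Treatment duration is already to be listed per subject, and the SAP amendment table mentions a rule for a missing last dose date, although the appendix holding it is not visible. Rates would not remove every obstacle to comparison with Fx-005, because subjects here have already completed a parent study.

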8.1.3. Analyses for Time to Event Endpoints

Kaplan-Meier estimates will be computed for all time to event endpoints, including median, interquartile ranges, and 95% confidence intervals. Kaplan-Meier curves will be presented at yearly intervals. These analyses will be provided by treatment group and by TTR mutation. Separate analyses will be conducted using both measurements of baseline, at study start and at active treatment start as specified above. Additionally, a set of analyses will be done for the time from onset of symptom.

8.2. Efficacy Analyses

The efficacy endpoints for this study are the cumulative efficacy data as measured by the Neuropathy Impairment Score (NIS); the Total Quality of Life (TQOL) score as measured using the Norfolk Quality of Life for Diabetic Neuropathy (QOL-DN) questionnaire; the Karnofsky Performance Scale Index; and the Modified Polyneuropathy Disability (mPND) score of ambulatory status.

The following measures will be analyzed using the methods described above for continuous outcomes in [Section 8.1.1](#): NIS-LL, TQOL, Karnofsky Performance Scale Index. These analyses will be provided by treatment group and by TTR mutation.

The assessment of subject ambulation will be analyzed using the methods described above for categorical measures in [Section 8.1.2](#). Due to the fact that there are two substantially different versions of the CRF page, the data will be summarized three ways: for the original CRF, for the revised CRF and for the combined recoded data. In addition, shift tables will be presented showing the distribution of subjects with a change in ambulation based on the combined recoded data. Finally, if there are sufficient numbers of subjects who demonstrate a change in ambulation stage, , then Kaplan-Meier estimates will be computed for the time to the next ambulatory stage (see details in [Appendix 1.8](#)). These analyses will be provided by treatment group and by TTR mutation.

8.3. Safety Analyses

Safety data will be summarized for the safety analysis population.

Treatment and Disposition of Subjects: Subject evaluation groups will show end of study subject disposition and will show which subjects were analyzed for efficacy, as well as for safety (adverse events and laboratory data). Frequency counts will be supplied for subject discontinuation(s) by treatment.

A listing of treatment duration for each subject will be reported in accordance with the sponsor reporting standards.

Demographic and Baseline Characteristics. A break-down of demographic data will be provided for age, gender, race, weight, body mass index, and height. Each will be summarized by treatment group, sex at birth and 'All Subjects' in accordance with the sponsor reporting standards. All baseline and disease characteristics will also be summarized.

Discontinuations. Subject discontinuations due to adverse events will be detailed and summarized.

Adverse events (AEs): Treatment emergent adverse events will be summarized by causality and severity.

Hematology, Biochemistry and Urinalysis: Descriptive statistics will be provided for each test result and for change from baseline by visit. Additional summaries for abnormalities in laboratory measures will be provided for the following populations: without regard to baseline, abnormal at baseline and normal at baseline.

Baseline is defined in two ways as described above.

ECG: Changes from baseline (defined as the last evaluation prior to the first dose of study drug) will be summarized for each of the ECG measures listed above. In addition, ECG changes from baseline will be categorized as follows:

- a change from baseline \geq 60 msec,
- a change from baseline \geq 90 msec;
- a change from baseline between 30 msec (inclusive) and $<$ 60 msec;
- a reading of greater than 450 msec at any visit;
- a reading of greater than 480 msec at any visit;
- a reading of greater than 500 msec at any visit.

Baseline is defined in two ways as described above.

Note: In Italy only Echocardiograms and Holter Monitoring were performed, and therefore, the Italian subjects will not be included in these summaries.

Vital signs: Will be summarized using descriptive statistics, to include: values at each visit, change from baseline to each visit and a categorization of clinically significant changes. A summary table of subjects experiencing orthostatic hypotension at each visit will be included. A table summarizing the subjects who experienced treatment emergent hypotension will be created.

Baseline is defined in two ways as described above.

Significant changes from baseline are defined as follows:

- Systolic Blood Pressure (mmHg) Decrease (Change \leq -20, or Value $<$ 90)
- Systolic Blood Pressure (mmHg) Increase (Change \geq 20, or Value $>$ 180)
- Diastolic Blood Pressure (mmHg) Decrease (Change \leq -15, or Value $<$ 50)
- Diastolic Blood Pressure (mmHg) Increase (Change \geq 15, or Value $>$ 105)
- Heart Rate (bpm) Decrease (Change \leq -15, or Value $<$ 50)
- Heart Rate (bpm) Increase (Change \geq 15, or Value $>$ 120)
- Weight (kg) Decrease (Change \leq -7%)
- Weight (kg) Increase (Change \geq 7%)

CCI

Concomitant medications: will be summarized.

Physical Examination: Results will be listed.

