V30M is the most common mutation associated with TTR-FAP, with major foci of patients in Portugal, Sweden and Japan. The disease usually begins in the third or fourth decade, but the onset of symptoms may be later, particularly in Sweden. Initial symptoms include decrease in temperature and pain sensation in the lower extremities; autonomic dysfunction, including orthostatic hypotension, gastrointestinal motility disorders, impotence, and urinary retention/incontinence. As the disease progresses to involve larger myelinated fibers, muscle weakness, loss of reflexes, and the impairment of position and vibratory sensations can occur. At this stage, involvement of upper extremities becomes apparent. Although penetrance varies greatly among geographic and ethnic foci, the outcome of TTR-FAP is invariably progressive and fatal. The length of survival for patients with TTR-FAP is severely shortened. After a mean interval of 10 years from initial symptom, patients usually

---

die from progressive and relentless worsening of the neuropathy, secondary infections, cachexia or sudden death. The only currently available disease-modifying treatment option is liver transplant.

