#### **7.5. Physical Examinations and Vital Signs**

The end of study physical examination (including weight) and vital sign assessments from Protocols Fx-006 and Fx1A-201 will serve as Day 0 (Baseline) for Protocol Fx1A-303/B3461023 if these examinations were performed within 30 days of Day 0. An abbreviated physical examination (including weight and vital signs) will be conducted at every other 6-month visit to the clinical unit.

For blood pressure and pulse, measurements will be taken lying and standing.

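### SAP 8.3 counts a blood pressure or heart rate already beyond a fixed limit at baseline as a significant change from baseline, even when it is unchanged or has moved towards normal

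*SAP*

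**What the plan says.** SAP 8.3 plans to summarise vital signs as "values at each visit, change from baseline to each visit and a categorization of clinically significant changes". The categories follow under "Significant changes from baseline are defined as follows". For blood pressure and heart rate each category has two parts joined by *or*:

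- "Systolic Blood Pressure (mmHg) Decrease (Change \leq -20, or Value $<$ 90"
- "Diastolic Blood Pressure (mmHg) Decrease (Change \leq -15, or Value $<$ 50"
- "Heart Rate (bpm) Decrease (Change \leq -15, or Value $<$ 50"

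The matching increase categories use changes of +20, +15 and +15, or values above 180, 105 and 120. Weight differs: "Weight (kg) Decrease (Change \leq -7" percent and its mirror image are pure change criteria.

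Elsewhere in SAP 8.3 the two ideas are kept apart. The ECG criteria list changes in msec and absolute readings (above 450, 480 and 500 msec) as separate items. Laboratory abnormalities are summarised three ways: for everyone, for those abnormal at baseline and for those normal at baseline.

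SAP 6.6 sets baseline as the last value before first study drug in Fx-005 or Fx1A-201, with a second baseline before active treatment for V30M subjects. Protocol 7.5 adds: "For blood pressure and pulse, measurements will be taken lying and standing". The visible list does not say which position it uses.

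**The concern.** The label promises change, but the value part of each criterion never looks at baseline. A subject who entered the parent study beyond a limit and stays there is reported as having changed.

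The study has no control group (Protocol 3.1), so change from baseline is the main way for a reader to separate what arose on tafamidis from what was there before. The disease also makes low blood pressure before treatment plausible: Protocol 1.2 lists "autonomic dysfunction, including orthostatic hypotension" among the initial symptoms. If some subjects start below a limit, the count of significant decreases is partly a count of baseline disease. The same reasoning applies at the high limits.

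**Working it through.** **Inputs.** The rules are from SAP 8.3, the baselines from SAP 6.6 and the visit schedule from Protocol 6.2.3 (nine annual visits, Months 12 to 108) and 6.2.4 (end of study). Neither document gives a vital-sign distribution or a within-subject SD, so those are assumed below. The plan states no figure of its own to reproduce.

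**Step 1: apply the rule literally.**

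| Baseline → visit | Change | Change part met | Value part met | SAP category | With a baseline condition |
|---|---|---|---|---|---|
| SBP 88 → 88 | 0 | no | yes | Decrease | none |
| SBP 85 → 89 | +4 | no | yes | Decrease | none |
| SBP 88 → 92 | +4 | no | no | none | none |
| SBP 92 → 88 | −4 | no | yes | Decrease | Decrease |
| SBP 120 → 100 | −20 | yes | no | Decrease | Decrease |
| DBP 48 → 48 | 0 | no | yes | Decrease | none |
| HR 48 → 48 | 0 | no | yes | Decrease | none |

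Unchanged and improved readings are called decreases. A baseline condition removes those and keeps the new fall below 90 and the 20 mmHg drop. One reading can also meet both directions: SBP 68 → 88 is an Increase by change (+20) and a Decrease by value (below 90). This is rare, at most 0.4% of readings in the scenarios of Step 3.

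**Step 2: how often the flag recurs.** Take a stable subject whose baseline equals the usual level b, with later readings normal around b and an assumed SD of 4 to 10 mmHg. For b below 90, the chance of a flag at one visit is Φ((90 − b)/SD). For b = 88 this is Φ(2/4) = 0.69 down to Φ(2/10) = 0.58. For b = 85 it is 0.89 to 0.69, and for b = 80 it is 0.99 to 0.84. The change part alone gives Φ(−20/SD), which is 0.00 to 0.02.

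If readings are independent, the chance of a flag at all nine annual visits is the ninth power: 0.04 to 0.01 at b = 88, 0.37 to 0.04 at b = 85, and 0.95 to 0.21 at b = 80.

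**Step 3: share of subjects flagged for an SBP decrease when nothing has truly changed.** Let baseline B and visit value V be normal with mean m and total SD s, with within-subject SD w. Their correlation is (s² − w²)/s², and V − B has SD w√2.

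- Baseline below 90: Φ((90 − m)/s), which is Φ(−2.00), Φ(−1.11) and Φ(−0.83).
- Change part alone: Φ(−20/(w√2)), which is Φ(−1.77) for w = 8 and Φ(−1.41) for w = 10.
- SAP rule: P(V − B ≤ −20 or V < 90).
- With the baseline condition: P(V − B ≤ −20, or V < 90 with B ≥ 90).

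The last two are integrated over the joint normal distribution of B and V.

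| Assumed m/s/w | Baseline < 90 | Change part alone | SAP rule | With condition | Difference, points (before rounding) |
|---|---|---|---|---|---|
| 120/15/8 | 2.3% | 3.9% | 5.7% | 5.0% | 0.8 |
| 110/18/10 | 13.3% | 7.9% | 18.5% | 12.1% | 6.4 |
| 105/18/10 | 20.2% | 7.9% | 24.5% | 13.5% | 11.0 |

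The relevant comparison is the SAP rule against the rule with the condition. Comparing with the change part alone would treat a new fall below 90 as an error. For the 110 subjects anticipated in Protocol 9.1, the difference is about 1 subject (110 × 0.008), 7 (110 × 0.064) or 12 (110 × 0.110) per reading. In the third scenario 5.7% of subjects are called a decrease by value with SBP at or above baseline.

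**The case against.** Combining a large shift with an extreme value is a reasonable screen, and this is one descriptive category in a study without hypotheses (SAP 4.1). SAP 8.3 also plans by-visit values and changes, a by-visit table of orthostatic hypotension and a table of treatment-emergent hypotension. SAP 6.3 limits treatment-emergent adverse events to those that begin after enrolment in this study or worsen during it. Text after the list is blacked out and may hold further handling, and the list of tables is in an addendum not seen here.

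Much of this stands. The offset is real but partial. By-visit mean changes do not show which counted subjects were already beyond a limit. The subject-level hypotension tables help only with low blood pressure, and nothing comparable is visible for slow pulse or for the high limits. Neither output corrects a category whose label and content disagree.

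A reader might infer more than the documents support:

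- **That affected subjects are flagged at every visit.** Vital signs are scheduled annually and at end of study, and the flag lapses when the reading crosses back. At a usual SBP of 88, Step 2 puts a flag at all nine annual visits at 0.01 to 0.04.
- **That the table produces safety signals.** The SAP calls these clinically significant changes, and they are descriptive.
- **That standing readings below 90/50 are expected before any drug.** Orthostatic hypotension is a postural fall; no baseline pressures are given, and nothing speaks to slow pulse at baseline.
- **That Tafamidis-Tafamidis and Placebo-Tafamidis will differ for this reason alone.** These are the randomised arms of Fx-005 (SAP 4.2), and no baseline imbalance in vital signs is shown. Protocol 1.2.4 describes the non-V30M patients as more severely affected, but SAP 6.5 analyses them separately.

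**Conclusion.** The concern holds as a misclassification in a stated rule. As written, the blood pressure and heart rate categories count a reading already beyond a limit at baseline as a significant change at any later vital-sign visit where it is still beyond that limit, whether it is unchanged or improved. That follows from the wording and needs no assumption.

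The size does need assumptions. It depends on how many subjects start beyond a limit, which the documents do not say. If about 2% start with SBP below 90, the excess is under one percentage point per reading. If 13% or 20% do, it is about 6 or 11 points. The two larger scenarios illustrate what the rule could do; no document supports those baseline shares. Efficacy results are not touched. The correction is worth making because it is cheap and follows the SAP's own practice for ECG and laboratory data.

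**What to change.** In SAP 8.3, for both baselines in SAP 6.6, count the value part of each criterion only when the baseline value was not already beyond that same limit. For example, SBP decrease becomes: change ≤ −20, or value < 90 with baseline ≥ 90. Apply the same condition to SBP > 180, DBP < 50 and > 105, and heart rate < 50 and > 120. The limits stay as they are. Show values beyond the limits regardless of baseline in a separate row not labelled as change.

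The cost is a wording change, one programming condition and one extra row for each limit, with no new data. The drawback is a lower count in the change category, by little or by a good deal depending on the baseline distribution. The separate row keeps every absolute value visible.
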